8.2 Methods for measurement of endpoints for clinical safety

See point 8.1. If there is any ambiguity in the evaluation the patient will be recommended to go to surgery to reduce the risk for insufficiently treated cancer.

9.0 HANDLING OF ADVERSE EVENTS

NOTE! In this study the following events are not reported as an AE or SAE:

- Planned surgery (e.g. TME surgery or stoma reversal)
- Planned hospitalization
- Recurrence
- Death due to progression of the disease

Any adverse events (AE) and serious adverse events (SAE) will be reported during the trial during the first year.

9.1 Definitions

9.1.1 Adverse Event (AE)

Adverse events are defined as any undesirable experience occurring to a subject during the study, whether or not considered related to the investigational product/the experimental treatment. Only adverse events reported spontaneously by the subject or observed by the investigator or his staff of grade 3 or 4 will be recorded.

9.1.2 Serious Adverse Event (SAE)

A serious adverse event is any untoward medical occurrence or effect that at any dose:

- results in death
- is life threatening (at the time of the event)
- requires hospitalisation or prolongation of existing inpatients' hospitalisation
- results in persistent or significant disability or incapacity
- is a congenital anomaly or birth defect
- is a new event of the trial likely to affect the safety of the subjects, such as an unexpected outcome of an adverse reaction, lack of efficacy of an IMP used for the treatment of a life-threatening disease, major safety finding from a newly completed animal study, etc.

SAEs that result in death or are life threatening should be reported expedited. The expedited reporting will occur not later than 7 days after the responsible investigator has first knowledge of the adverse reaction. This is for a preliminary report with another 8 days for completion of the report.

All SAEs, irrespective of relationship to the study treatment must be reported to the Datacentre.

The SAE report should include the investigator's assessment of causality. If follow-up information changes the investigator's assessment of causality, this should be noted on the SAEs occurring within 30 days after discontinuation of the study treatment should be reported.

9.1.3 Suspected Unexpected Serious Adverse Reaction (SUSAR)

Adverse reactions are all untoward and unintended responses to an investigational product

836 related to any dose administered.

837 Unexpected adverse reactions are adverse reactions, of which the nature, or severity, is not
838 consistent with the applicable product information (e.g. Investigator's Brochure for an
839 unapproved IMP or Summary of Product Characteristics (SPC) for an authorised medicinal

840 9.2 Assessment of Adverse Events (AE)

841 9.2.1 Assessment of causal relationship

842 The investigator is responsible for determining whether there is a causal relationship between
843 the AE/SAE and use of the investigational medicinal product.

844 Consideration should be given to whether there is a reasonable possibility of establishing a
845 causal relationship between the adverse event and the investigational medicinal product based
846 on the analysis of the available evidence.

847 All AE can be categorized as either likely related, possibly related, unlikely related or not
848 related, in accordance with the definitions below:

849 **Likely related:** Clinical event, including abnormal results from laboratory analyses, occurring
850 within a reasonable time after administration of the intervention/investigational medicinal
851 product. It is unlikely that the event can be attributed to underlying disease or other
852 medications but is most likely caused by the investigational medicinal product and its
853 emergence is reasonable in relationship with use of the investigational medicinal product.

854 **Possibly related:** Clinical event, including abnormal results from laboratory analyses,
855 occurring within a reasonable time after administration of the intervention/investigational
856 medicinal product. The event could be explained by the investigational medicinal product,
857 and its emergence is reasonable in relationship with use of the investigational medicinal
858 product, but there is insufficient information to determine the relationship. The event could be
859 explained by an underlying disease or other medications.

860 **Unlikely related:** Clinical event, including abnormal responses from laboratory tests, unlikely
861 to be related to the intervention/investigational medicinal product and can be reasonably
862 explained by other medication or underlying disease.

863 **Not related:** Clinical event, including abnormal results from laboratory analyses, that is not
864 reasonably related to the use of the intervention/investigational medicinal product.

865 Those AEs which are suspected of having a causal relationship to the investigational
866 medicinal product will be followed up until the subject has recovered or is well taken care of
867 and on the way to good recovery (see also section **Error! Reference source not found.,**
868 **Error! Reference source not found.**).

869 If the reporting investigator does not provide any information on causality, the sponsor should
870 consult with the reporting investigator and encourage the expression of a position on this
871 issue. The sponsor must take into account the assessment of causality provided by the
872 investigator. If the sponsor disagrees with the investigator's assessment of causality, both the
873 investigator's and the sponsor's views should be included in the report.

9.2.2 Assessment of intensity

Patients should be reviewed at least weekly during CRT to perform an assessment of acute toxicity. Remote toxicity assessments (e.g. over the telephone) are allowed as per local practice 4. The local team should have a structure in place that ensures that patients experiencing side effects can be seen and undergo review.

The following guidance should be followed for the management of acute toxicity and dose modifications:

- Adverse Events (AEs) should be graded according to the NCI Common Terminology Criteria for Adverse Events version 4.03 (CTCAE v4.03)
- In the event of overlapping toxicities, dose modification should be based on the worst toxicity grade observed.
- All dose modifications should be documented with clear reasoning and documentation of the approach taken in the CRF and in the medical notes.
- If a patient experiences a toxicity, then dose modifications should be applied as specified in the protocol section 8.3.7.
- **In the event of a second episode of the same grade ≥ 3 toxicity, capecitabine should be permanently discontinued.**

Dose modification and toxicity should be managed according to local routines. Details on toxicity is registered in CRF.

9.3 Reporting and registration of Adverse Events

NOTE! In this study the following events are not reported as an AE or SAE:

- Planned surgery (e.g. TME surgery or stoma reversal)
- Planned hospitalization
- Recurrence
- Death due to progression of the disease

At each trial visit, adverse events (AE) are registered, starting after study start, up to and including one year after the subject has entered the study. All AE that occurs during the trial and which are observed by the investigator/trial nurse or reported by the subject will be registered in the CRF regardless of whether they are assessed as related to the investigational medicinal product or not. Assessment of causal relationship, severity, and whether the AE is considered to be an SAE will be made by the investigator directly in the CRF. At minimum for each AE/SAE, a description of the event is recorded (diagnosis/symptom if diagnosis is missing), start and stop dates, causal relationship, severity, if the AE is considered to be an SAE, measures and outcome.

9.3.1 Reporting of Adverse Events (AE)

All AE shall be registered in the CRF within 72 hours.

9.3.2. Reporting of Serious Adverse events (SAE)

Serious Adverse Events (SAE) are reported to the sponsor on a special SAE form within 24 hours of the investigator being informed of the SAE.

Follow-up information describing the outcome and handling of the SAE is reported as soon as this information is available. The original SAE form should be kept in the Investigator Site File.

9.3.2. Reporting of Suspected Unexpected Serious Adverse Reactions (SUSAR)

Those SAE which are assessed by sponsor to be SUSAR are to be reported to the EudraVigilance database. The completed CIOMS form will be the basis for the reporting, by Swedish Medical Products Agency in the EudraVigilance database according to the specified time frames.

SUSAR that are fatal or life-threatening are reported as soon as possible and no later than 7 days after the SAE has become known to the sponsor. Relevant follow-up information is sent thereafter within an additional 8 days. Other SUSAR are reported as soon as possible and no later than 15 days after they have come to the sponsor's knowledge.

Information about SUSAR occurring during the trial is compiled by the sponsor and sent to the principal investigators at all participating sites.

9.4 Follow-up of Adverse Events

All adverse events will be followed until they have abated, or until a stable situation has been reached. Depending on the event, follow up may require additional tests or medical procedures as indicated, and/or referral to the general physician or a medical specialist.

9.5 Independent Data Monitoring Committee

As the study is not randomized low intervention study a formal safety committee will not be appointed.

9.6 Annual Safety Report (ASR)

Since the sponsor is non-commercial and the marketing authorization holder of the investigational medicinal product is within the EU/EEA the SPC is used as RSI. The simplified template of Annual Safety Report will be used for the ASR reporting.

9.7 Procedures in case of emergencies, overdose or pregnancy

Medication errors, pregnancy and use of other medicinal products than those specified in the protocol, including misuse and abuse of the investigational medicinal product, shall be subject to the same reporting obligations as adverse reactions.

If an unforeseen event is likely to have a serious impact on the benefit/risk relationship of the trial, the sponsor and investigator should take appropriate Urgent Safety Measures (USM) necessary to protect the subjects. Examples of such measures are to temporarily halt the clinical trial or to introduce supplementary monitoring measures. The sponsor should, via CTIS, inform the concerned Member States about the event and the measures taken. Notification must be made as soon as possible, but no later than seven days after the measures have been taken.

949 If a subject or partner to a subject who participates in a clinical trial, becomes pregnant, this
950 person will be followed up until the birth has taken place. If the foetus/child has any
951 congenital malformation, this must be reported as a serious adverse event (SAE).

952 **10 STATISTICS**

953 **10.1 Analysis population and statistical analyses including sample size** 954 **calculations**

955 A statistical analysis plan will be developed for the primary endpoint before start of inclusion and for all secondary endpoints before analysis. Descriptive statistical methods will be used to present data, and assuming a non-normally distributed data non-parametric statistics will be used.

956 Using a sample size of 82, the critical number of successes is 49. If 49 or more patients achieving complete response at one year, the null hypothesis will be rejected at alpha 0.05. Conversely, if 34 or more patients have negative response, then the null hypothesis cannot be rejected. If at any time 49 complete responses or 34 negative responses are observed, rejection/failure to reject is known with 100% certainty. However, we plan to include patients until the randomized controlled trial STAR-TREC continues follow-up.

957 **11 QUALITY CONTROL AND QUALITY ASSURANCE**

958 **11.1 Quality Assurance and Sponsor oversight**

959 The sponsor's quality-related work is based on a risk analysis of the trial as a whole: design,
960 conduct, data collection, evaluation, reporting and archiving. The sponsor will perform quality
961 assurance and quality control activities for the trial; however, responsibility for the accuracy,
962 completeness, and reliability of the trial data presented to the sponsor lies with the PI (and
963 delegate(s)) generating the data.

964 **11.2 Monitoring**

965 The trial will be monitored by an independent monitor before the trial begins, during the
966 conduct of the trial, and after the trial has been completed. This is to ensure that the trial is
967 carried out according to the protocol and that data is reliably and robust and are collected,
968 documented, and reported according to ICH-GCP and applicable ethical and regulatory
969 requirements. Monitoring will be risk-based, which means that the extent of the monitoring is
970 based on the sponsor's risk-assessment and is performed as per the trial's monitoring plan,
971 The monitoring is intended to ensure that the subject's rights, safety, and well-being are met
972 and that data in the CRF are complete, correct, and consistent with the source data.

973 **11.3 Source data**

974 The investigator must keep source documents for each subject in the trial. A document
975 describing what has been classified as source data in the trial (source data reference
976 document) should be included in the Investigator Site File (ISF). The investigator must ensure
977 that all source documents are accessible for monitoring and other quality control activities.

978 Source data is defined before trial start at each individual site and can, in cases where source
979 data is not registered in another document, consist of the CRF. This should be decided in
980 consultation with the monitor and clearly stated in the source data reference document.

Access to trial-related documentation, such as subjects' medical records, data acquisition tools (DATs) (including CRFs), other source data and other trial documentation will be provided for monitoring and auditing purposes. Access to subjects' medical records will require a confidentiality agreement to be signed by the person in charge of the medical records at the trial site and by the monitor and auditor, if applicable. Access will also be granted in the context of regulatory inspections.

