Primary endpoint:	Clinical complete response rate evaluated by MRI and endoscopy at one year (i.e. patients that have not undergone surgery)
Secondary endpoint:	
 • Oncologic: 
 ○ Clinical complete response rate without surgical intervention at three years ○ Local recurrence at three years ○ Mortality at three years ○ Overall survival at three years • Surgical 
 ○ Surgical morbidity measured as Comprehensive Complications index at 90 days after surgery (if performed) ○ Total length of hospital stay during the first year ○ Outcome after surgery (Histopathological assessment of the resected rectal specimen to report (a) Presence of clear margins (>1mm from excision border to tumour edge), (b) TNM staging.) • Patient reported outcomes (all measured Baseline, post treatment, at surgery if applicable and at one, two and three years) 
 ○ Quality of life ○ Urinary function ○ Sexual function ○ Bowel and stoma function 
Health economic analysis at three years

Trial design:	
National, multi-centre, open-label, prospective trial.
 
Patients will choose possible organ preservation or standard surgery.
 
Those who prefer possible organ preservation will be offered treatment according to the experimental arm of the STAR TREC trial: mesorectal Chemoradiotherapy (CRT).
 
Those who prefer standard surgery or have no preference will undergo standard Total Mesorectal Excision (TME) surgery without neoadjuvant radiotherapy treatment.

Trial population:	Subjects referred to either a colorectal surgeon or the colorectal cancer multidisciplinary team (MDT) with suspected early stage rectal cancer (T1-T3bNx/N0). Diagnosis must be confirmed with a biopsy prior to study entry.
Number of subjects:	Due to the study design the number of patients to be included has not been fixed, but it is estimated to be at least 60-80 patients during the period until STAR-TREC data will be available
Inclusion criteria:	
 • Biopsy proven adenocarcinoma of the rectum < 12 cm • Magnetic Resonance Imaging (MRI)-staged TT1-3b, N0, MX/M0 rectal tumour • MDT determines that the following treatment options are all

	
reasonable and feasible: TME surgery or CRT
 
 • Eastern Cooperative Oncology Group (ECOG) performance status 0-1 • Willing and able to consent

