beam radiotherapy (9 Gy \times 5) or brachy radiotherapy (90Gy/3 fractions). They found that 64% of patients with external beam radiotherapy achieved a clinical complete response, compared to 92% after brachy radiotherapy. The 5-year local regrowth was 39% vs 17%, and some patients had their local regrowth after 3 years, indicating that long-term follow-up may be necessary. There are indications that patients that undergo brachy radiotherapy and then have incomplete response have very poor bowel function suggesting that studies are required to ascertain that patients receive correct information for shared decision making (38).

In summary there seems to be sufficient evidence that some patients will achieve clinical complete response after chemoradiotherapy with a long-term positive oncologic outcome (25), but long-term morbidity is not sufficiently described to date. This treatment will increase the risk for postoperative complications and increased risk for affected bowel function after both local excision and TME-surgery. Local excision may not always be adequate to treat insufficient response to chemoradiotherapy. Presently in Sweden there are no available treatment options apart from radical surgery (as recommended in the Swedish National Treatment Guidelines for Colorectal cancer) for patients with early rectal cancer while waiting for the long-term results from the STAR-TREC trial. The CORRECT trial has commenced in Stockholm and Uppsala in 2025 offering treatment options with contact therapy (brachy radiotherapy).

2.4 Rationale and design of the Next generation study awaiting the results from the STAR-TREC study

In light of the promising results from smaller studies, and the positive experience from treatments centres within the STAR-TREC trial this study aims to offer a treatment option to patients with early rectal cancer in a prospective phase II study to enable evaluation of results, and to enable comparisons with results from present and future studies until results from the STAR-TREC trial are published. The first results presented at ESTRO 2025 indicate that 57% of patients that received CRT maintained a clinical complete response one year after treatment compared to 27.3% in the arm with 5 \times 5 Gy (<https://user-swndwmf.cld.bz/ESTRO-2025-Abstract-Book>). The dosage of Capecitabine at 825mg/m² for five days per week has been chosen to mimic the STAR-TREC study.

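### The 49/34 decision rule is calibrated to 82 patients, but the protocol leaves the number open and does not say how the rule applies to any other number

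*Protocol*

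**What the plan says.** Section 10.1 gives one decision rule for the primary endpoint: "Using a sample size of 82, the critical number of successes is 49". It then says "If 49 or more patients achieving complete response at one year, the null hypothesis will be rejected at alpha 0.05", and for the other side "Conversely, if 34 or more patients have negative response, then the null hypothesis cannot be rejected". Both counts are treated as final whenever they occur: "If at any time 49 complete responses or 34 negative responses are observed, rejection/failure to reject is known with 100% certainty". The paragraph ends by leaving inclusion open: "However, we plan to include patients until the randomized controlled trial STAR-TREC continues follow-up".

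The synopsis, under number of subjects, does not give 82. It says "the number of patients to be included has not been fixed, but it is estimated to be at least 60-80 patients", and does not say whether that estimate counts only patients who choose CRT or also those who choose surgery.

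Section 10.1 states neither the null rate nor whether the test is one-sided. Section 4.0 sets the aim of a complete response rate of 50% or more. Sections 4.3 and 8.1.1 define the endpoint among patients managed non-operatively at onset.

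**The concern.** A critical count belongs to one sample size. Here the count is fixed while the sample size is not. The synopsis expects a number that may be below 82, and section 10.1 allows one above it. The protocol gives no cut-off for any other number and does not restrict the test to the first 82 CRT patients.

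This is the only decision rule stated for the primary endpoint. The study is open-label, section 9.5 appoints no monitoring committee, and the final number depends on the timing of another trial. If the rule is not tied to a number in advance, the verdict could turn on which number or which reading is chosen once results are visible.

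**Working it through.** **Inputs.** N = 82, 49 responses, 34 negatives and alpha 0.05 come from section 10.1. The null rate p0 = 0.50 is inferred from section 4.0. The rate 0.57, used only to illustrate, is the STAR-TREC figure in section 2.4: "57% of patients that received CRT maintained a clinical complete response one year after treatment".

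**Formula.** P(X ≥ k | N, p) = Σ from j = k to N of C(N, j) p^j (1 − p)^(N − j). The proper cut-off at N is the smallest k with P(X ≥ k | N, 0.50) ≤ 0.05.

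**The protocol's own figure.** P(X ≥ 49 | 82, 0.50) = 0.0485 and P(X ≥ 48 | 82, 0.50) = 0.0753. So 49 is the one-sided 5% cut-off at 82; a two-sided 5% test would need 51. The failure count fits too: 82 − 49 + 1 = 34. The rule is therefore reproduced, on a one-sided reading against 50%.

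**Holding 49 fixed and varying N, if 49 is applied to all patients analysed:**

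| N | P(reject) at 50% | P(reject) at 57% | Proper cut-off (its level) | P(reject) at 57% with proper cut-off |
|---|---|---|---|---|
| 60 | <0.0001 | <0.001 | 37 (0.046) | 0.276 |
| 70 | 0.0005 | 0.018 | 43 (0.036) | 0.266 |
| 80 | 0.028 | 0.257 | 48 (0.046) | 0.336 |
| 81 | 0.037 | 0.302 | 49 (0.037) | 0.302 |
| 82 | 0.0485 | 0.349 | 49 (0.0485) | 0.349 |
| 83 | 0.062 | 0.398 | 50 (0.039) | 0.315 |
| 90 | 0.230 | 0.725 | 54 (0.036) | 0.321 |
| 100 | 0.618 | 0.956 | 59 (0.044) | 0.383 |

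**Below 82.** At N = 80, 48 responses are significant (P = 0.046) but miss 49. The rule can also be silent. Failure to reject needs 34 negatives, that is, at most N − 34 responses, so anything from N − 33 to 48 responses meets neither boundary. At N = 70 that is 37 to 48 responses. At a true 57% the chance of no verdict is 98% at N = 60, 78% at 70 and 16% at 80.

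**Above 82.** Because 49 + 34 = 83, both boundaries can be met in the same data from N = 83 on. At N = 90 this happens with 49 to 56 responses, since 90 − 56 = 34. At N = 100, 49 responses is an observed 49%, below the null, yet it meets the rejection count.

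**If the rule is locked.** Among the first 82 patients exactly one of two things is true: at least 49 responses, or at least 34 negatives. Counting in order of registration, reaching 49 responses before 34 negatives is the same event as at least 49 responses in the first 82. The type I error is then 0.0485 however many patients follow.

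**The case against.** The strongest reply is that the rule opens with a sample size of 82, and that the sentence about certainty at any time is ordinary curtailment: with 82 patients, 49 responses or 34 negatives settle the result. The sentence on continued inclusion can then mean that patients are still offered treatment after the test is decided. On that reading the certainty sentence is true and the error stays at 0.0485. The reading is as natural as the other, but the protocol does not state it, and the sentence that follows the rule begins by qualifying it.

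Three stronger conclusions are tempting and are not supported:

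- A reader might infer that alpha 0.05 holds only if exactly 82 are analysed. It does not: the error is at or below 0.05 for every N up to 82, and 49 is also the proper cut-off at 81. Below 82 the harm is lost power or no verdict.
- A reader might infer that the rule as written has a type I error anywhere from near 0 to near 1. The high values arise only if 49 is detached from 82 and applied to all patients, which the text neither instructs nor excludes.
- A reader might add that the chance of rejecting at a true 57% is only 35% even at 82. That is correct arithmetic but a separate matter: the protocol states no alternative rate and no power.

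It is also fair that the synopsis figure is a floor, so it is compatible with 82, and that the endpoint definition already limits the test to non-operative patients. Only the recruitment estimate is ambiguous on that point. Finally, section 10.1 promises a statistical analysis plan for the primary endpoint before inclusion starts, and sidedness or a cut-off by N could be placed there. But the protocol itself fixes the counts and the alpha while leaving the number open, and these statements need reconciling where they stand.

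**Conclusion.** The point holds in this form. The 49/34 rule is valid at N = 82. Below 82 it keeps alpha but is too strict or undecided (at 81, 49 is still the proper cut-off). Above 82 it is valid only under a restriction to the first 82 patients, or to the first boundary reached, that the protocol does not state. Without that restriction the type I error passes 0.05 at once and reaches 0.23 at 90 patients.

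The figures assume a 50% null and a one-sided test, both inferred; they are the natural reading because they reproduce 49 of 82. They also assume independent patients with a common response rate. The 57% serves only as an illustration taken from the protocol's background. If the synopsis estimate includes patients who choose surgery, the CRT number is smaller and the loss below 82 is larger.

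**What to change.** In section 10.1, state the null rate of 50% and that the test is one-sided at 0.05. Then choose one of these before the first inclusion:

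- **(a) Lock the counts.** Apply 49/34, and the sentence on certainty at any time, only to the first 82 consecutively registered CRT patients. Report later patients descriptively. If fewer than 82 are available, use the exact binomial cut-off for the actual number (for example 37 of 60, 43 of 70, 48 of 80).
- **(b) Drop the counts.** Use a one-sided exact binomial test against 50% at the final number of CRT patients, carried out once when the last one-year status is known (for example 54 of 90, 59 of 100). Delete the sentence on certainty at any time.

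Under either option, align the number in the synopsis with section 10.1 and say that it counts CRT patients. The cost is protocol and analysis-plan wording only; no extra patients are needed.
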